#### **Specific Data Collection Includes:**

Clinical Data: Enrollment characteristics including age, race, sex, smoking history, prior spirometric data (FEV1, FEV1% predicted, FVC, FVC % predicted, FEV1/FVC), exacerbation history, enrollment inhaler regimen, self-reported frequency of albuterol use, baseline CAT score

Data Collection Tools: Enrollment questionnaire, CAT questionnaire, monthly AECOPD and self-reported albuterol use questionnaire, and Digihaler device. The Digihaler uses integrated sensors to capture inhalation data and stores it onto an e-module inside the device. When within range, the e-module transfers the stored data using Bluetooth technology to a paired app on the users' phone. The app can display the data in various reports as well as export the reports in the form of pdfs which can be emailed. The app also shares the data to a server via a wifi connection which enables real-time data sharing to a provider facing dashboard. The data the provider sees is the same as what patients see and also have the ability to be exported into a .csv file for further analysis. For additional data points, beyond what the patient and provider currently see, our team has the ability to export more information in the form of data extracts from the back end cloud server. This can be setup to send at a predetermined interval for further analysis.

**Patient Reported Outcomes (PROs):** CAT questionnaire, self-reported monthly average albuterol use during study, daily self-assessment asking “How are you feeling?” with responses provided on a Likert scale on the DAQ app, and Dihaler metric algorithm-triggered symptom questions using the DAQ app.

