The DAQApp provides patients with a Privacy Notice within the App explaining Teva's policies and practices for handling information and the choices that patients can make about the how their information is collected and used. Information that is collected and its use is described in detail in the Privacy Notice. Patients must accept the privacy notice within the App and provide in-App consent to store their information in a cloud prior to using the App functionality. Information stored may include inhalation events, inhalation metrics as well as DAQ App diagnostic data. Patients must also provide a separate consent to share their information with a specific healthcare provider or research study site by signing up to a restricted access "Healthcare Program" within the DAQ App. A healthcare provider or research study personnel can view the information via a web-based application, the Digihaler® Dashboard.

Teva has enacted commercially reasonable physical, technical, and administrative safeguards to secure information that is collected and stored on the Teva Digital System, which includes the App, the dashboard and the cloud. To prevent unauthorized access to their personal information, the App or any portion thereof, to maintain information accuracy, and to ensure the correct use of information, patients are strongly encouraged to password protect their device and refrain from providing any third party with unsupervised access to their device.

---

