## 6.2 STUDY INTERVENTION COMPLIANCE

Compliance with study interventions will be ensured by the study team during monthly.

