## 8 STUDY ASSESSMENTS AND PROCEDURES

No study results will be specifically distributed to the study subject.

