## 9 STATISTICAL CONSIDERATIONS

### 9.1 HYPOTHESIS

We hypothesize that inhaler metrics (PIF, inhalation volume, rescue inhaler use) will vary among COPD populations. We also hypothesize that increased albuterol use will positively correlate with worse daily Leikert scores, declining PIF, lower inhalation volume and higher CAT scores. We hypothesize that self-reported albuterol use will be lower than actual albuterol use captured by the DAQ app. We hypothesize that increased albuterol use will positively correlate with more symptomatic DAQ responses. The proposed study is designed to yield an initial exploration of the metrics captures by the Digihaler in a COPD population.

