### 9.4 STATISTICAL ANALYSES

Below are the pre-specific outcome measures:

Primary Outcome Measure:

1. Variability in Peak Inspiratory Flow (PIF) Measured via Digihaler Device (Time Frame: Three months)
  - b. PIF is the maximal flow occurring during an inhalation effort, expressed in Liters/minute. Mean, standard deviation and coefficient of variation (calculated by dividing standard deviation of PIF by the mean of the PIF) of daily PIF measurement collected over three months will be calculated. PIF will be measured using the Digihaler device.

Secondary Outcome Measures:

1. Correlation of Self-Reported Inhaler Use with Actual Inhaler Use (Time Frame: 3 months)

- a. Correlation between self-reported inhaler use and actual inhaler use over three months will be calculated with Spearman rank-order correlation coefficient. Self-reported inhaler use will be determined with an investigator-developed single question categorizing average use over the last four weeks with five groups (not at all, once a week or less, two or three times a week, one or two times a day, three or more times a day). Actual inhaler use will be directly measured via Digihaler device and categorized into one of the five groups described above.
2. Variability in Inhalation Volume Measured via Digihaler (Time Frame: Three months)
  - a. Inhalation volume is the volume of air inspired during an inhalation effort, expressed in Liters. The mean, standard deviation and coefficient of variation (calculated by dividing standard deviation of inhalation volume by the mean of the inhalation volume) of daily inhalation volume measurements collected daily over three months will be calculated. Inhalation volume will be measured using the Digihaler device.

The primary analysis will be descriptive, with analytical plans as defined above for each primary and secondary outcome.

The primary analysis will be descriptive, with analytical plans as defined above for each primary and secondary outcome.

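### Nothing keeps the monthly albuterol recall item independent of the inhaler record that participants can see in the app, so recall may look more accurate than it is

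*Combined protocol and SAP*

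**What the plan says.** Under Specific Data Collection, section 6.1.1 describes how inhalation data pass from the device to a paired app on the participant's phone. It says "The app can display the data in various reports". The upload to a server "enables real-time data sharing to a provider facing dashboard", and "The data the provider sees is the same as what patients see". Section 2.3.1 lists inhalation events among the information that may be stored. It adds, for participants who have separately consented to sharing: "A healthcare provider or research study personnel can view the information via a web-based application".

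Participants are sent into the app every day for the self-assessment (sections 1.1, 4.1 and 6.1.1). At the monthly contact they are asked about average albuterol use over the preceding month, which section 6.1.1 treats as recall. For the analysis, section 9.4 states: "Self-reported inhaler use will be determined with an investigator-developed single question categorizing average use over the last four weeks". There are five ordered groups. Device-recorded use is sorted into the same groups, and the two are compared by Spearman correlation. The direction expected is in section 9.1: "We hypothesize that self-reported albuterol use will be lower than actual albuterol use captured by the DAQ app".

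No section restricts the display of use counts, tells participants to answer without the app, keeps the caller unaware of the dashboard, or fixes the order of questions on the call.

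**The concern.** The comparison is informative about recall only if the recall answer is formed without sight of the record it is compared with. Section 2.2 justifies electronic capture partly on the ground that patients often misreport their use. A participant who reads the record before answering no longer shows that misreporting. Good apparent recall could then reflect the app and not memory, and no item collected in the study would separate the two. At stake are the interpretation of secondary outcome 1 and of the under-reporting hypothesis in section 9.1. The primary outcome, variability of PIF, is untouched.

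**Working it through.** The documents give no target correlation, precision or consultation rate to reproduce. Section 9.2 states that there is no power calculation, and the sample is 60. The check is therefore in three steps: what follows by algebra, what needs assumed values, and how that compares with sampling error.

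**1. Algebra.** Let f be the fraction of participants who read the app and report the recorded category exactly. Let A be exact agreement and U the share reporting a lower group than the device, both when nobody consults. If consulting is unrelated to recall accuracy:

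- Observed agreement = f + (1 − f) × A, which is at least A.
- Observed under-reporting share = (1 − f) × U, which is at most U.

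So the direction is fixed for these two measures. With A = 43%, U = 49% and f = 0.5, agreement is 0.5 + 0.5 × 0.43 = 0.715, about 71%, and under-reporting is 0.5 × 0.49 = 0.245, about 25%.

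**2. Simulation, for Spearman.** Spearman has no such fixed direction. The assumptions, none of them from the documents, are:

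- 200,000 simulated participants, with actual use log-normal and log-SD 1.2.
- Median use of 10 or 7 per week.
- The gaps between the five groups closed at 0.25, 1.5, 5 and 17.5 uses per week.
- Recall equal to actual use times a multiplier times log-normal error.

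| Median per week | Recall multiplier | Error log-SD | Spearman, f = 0 | Spearman, f = 0.5 |
|---|---|---|---|---|
| 10 | 1.0 | 1.0 | 0.67 | 0.83 |
| 10 | 0.5 | 1.0 | 0.69 | 0.80 |
| 7 | 0.7 | 0.7 | 0.78 | 0.88 |
| 7 | 0.7 | 1.0 | 0.69 | 0.83 |
| 7 | 0.25 | 0.3 | 0.88 | 0.81 |

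The coefficient rises in the first four rows and falls in the last. When everyone under-reports strongly and consistently, ranks are well preserved without the app, and correcting only half of the participants disturbs them. In that last row exact agreement still rises, from 11% to about 56%.

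**3. Sampling error at n = 60.** By Fisher's z, the standard error is 1/√57 = 0.132. For a coefficient of 0.7, z = 0.867, and 0.867 ± 1.96 × 0.132 gives a 95% interval of 0.54 to 0.81, a half-width of about 0.135. In the first two rows the shifts are 0.83 − 0.67 = 0.16 and 0.80 − 0.69 = 0.11. Both are close to that half-width, so such a shift could not be recognised from the study's own data.

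**The case against.** The strongest reply is that the documents show opportunity and not use. The app can display reports, but no section says that participants open them before the call, or that the reports give a four-week average. This stands. A reader might infer that self-report is contaminated and agreement is overstated; the documents support only that they may be.

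A reader might also infer that the coordinator reviews the dashboard and corrects the answer. That is not in the text. Dashboard access depends on the participant's sharing consent. The schedule row on inhaler use and compliance (section 1.3) is also ticked at screening, before any device is mailed, so it need not mean a check of device data. Section 6.2, "Compliance with study interventions will be ensured by the study team during monthly", breaks off and mentions neither device nor dashboard. The staff route is possible but weaker than the participant's own access.

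Third, other features also produce disagreement. The Digihaler is only the primary mode of SABA therapy, and section 6.3 disallows no medication. Albuterol taken by another route can be recalled but not recorded. That can lower agreement while also masking under-reporting. It is a separate error and cannot be assumed to cancel this one, but it leaves the net direction for agreement unknown.

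Finally, section 8 says "No study results will be specifically distributed to the study subject". One might read this as a contradiction of the app display, or as a safeguard. It is neither: it concerns distribution of results by the study and does not restrict the app. No correction there is needed.

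**Conclusion.** The gap holds as a missing safeguard: the plan as written leaves the monthly recall item open to influence from the record it is compared with. For any consultation that occurs, the gain in exact agreement and the loss of apparent under-reporting are firm in direction. A rise in Spearman is likely but not assured, so a claim that the planned coefficient must be inflated goes too far. The size is unknown. The halving of under-reporting shown above follows almost directly from assuming that half consult and report the recorded category exactly, and the documents give no such rate. The point concerns one secondary outcome of a descriptive pilot. It is worth acting on because the remedy is cheap and the problem cannot be diagnosed afterwards from the data planned.

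**What to change.** In section 6.1.1 and the monthly call script:

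1. Ask the four-week albuterol-use item first, and record the answer before any dashboard data are opened or discussed.
2. Instruct the participant to answer from memory without opening the app.
3. Add one yes/no item: whether the participant looked at their inhaler-use record in the last four weeks.

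In section 9.4, report secondary outcome 1 overall and, as supportive only, in those answering no. State that the overall result applies to patients with access to their own record.

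The cost is one extra item, a fixed question order and one more line of analysis. The subgroup answering no will be self-selected and smaller than 60 if anyone answers yes, so its estimate will be imprecise and should not replace the overall result. If calls have already been made, the statement about access to the record can still be added.

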## 6.1.2 DOSING AND ADMINISTRATION

ProAir Respclick will be dosed and administered in accordance with the package insert ([https://www.accessdata.fda.gov/drugsatfda\\_docs/label/2015/205636s000lbl.pdf](https://www.accessdata.fda.gov/drugsatfda_docs/label/2015/205636s000lbl.pdf)). Specifically, albuterol sulfate 117 mcg will be administered 2 inhalations repeated every 4 to 6 hours as needed.

## 6.2 STUDY INTERVENTION COMPLIANCE

Compliance with study interventions will be ensured by the study team during monthly.

## 6.3 CONCOMITANT THERAPY

For this protocol, a prescription medication is defined as a medication that can be prescribed only by a properly authorized/licensed clinician. There will be no disallowed medications in this study.

# 7 STUDY INTERVENTION DISCONTINUATION AND PARTICIPANT DISCONTINUATION/WITHDRAWAL

## 7.1 DISCONTINUATION OF STUDY INTERVENTION

If a clinically significant finding is identified (including, but not limited to changes from baseline) after enrollment, the investigator or qualified designee will determine if any change in participant management is needed. Any new clinically relevant finding will be reported as an adverse event (AE).

The data to be collected at the time of study intervention discontinuation will include the following:

- Reason for discontinuation
- Vital signs, if available
- Related medical records, if available

## 7.2 PARTICIPANT DISCONTINUATION/WITHDRAWAL FROM THE STUDY

Participants are free to withdraw from participation in the study at any time upon request. An investigator may discontinue or withdraw a participant from the study for the following reasons:

- Significant study intervention non-compliance
- If any clinical adverse event (AE), laboratory abnormality, or other medical condition or situation occurs such that continued participation in the study would not be in the best interest of the participant
- Disease progression which requires discontinuation of the study intervention
- If the participant meets an exclusion criterion (either newly developed or not previously recognized) that precludes further study participation

The reason for participant discontinuation or withdrawal from the study will be recorded in the study file. Subjects who sign the informed consent form but who do not receive the study intervention may be replaced. Subjects who sign the informed consent form, and receive the initial study intervention, and subsequently withdraw, or are withdrawn or discontinued from the study, will also be replaced, to ensure 60 complete adult data sets.

### 7.3 LOST TO FOLLOW-UP

A participant will be considered lost to follow-up if he or she is not able to be contacted on phone visit and no-longer is transmitting data via the DAQ app.

The following actions must be taken if a participant cannot be contacted:

- The site will attempt to contact the participant and reschedule the missed phone contact within 1 week and counsel the participant on the importance of maintaining the assigned visit schedule and ascertain if the participant wishes to and/or should continue in the study.
- Before a participant is deemed lost to follow-up, the investigator or designee will make every effort to regain contact with the participant (where possible, three telephone calls). These contact attempts should be documented in the participant's study file.
- Should the participant continue to be unreachable, he or she will be considered to have withdrawn from the study with a primary reason of lost to follow-up.

## 8 STUDY ASSESSMENTS AND PROCEDURES

No study results will be specifically distributed to the study subject.

### 8.1 OUTCOME ASSESSMENTS

- Digihaler PIF: mean, median, standard deviation
- Digihaler Inspiratory volume: mean, median, standard deviation
- Digihaler Inhaler usage: count
- Self-reported inhaler usage: Average use over the preceding month
- COPD Assessment Test (CAT) questionnaire: Collected monthly
- Self-report of COPD exacerbation events on study
- Responses to daily self-assessment asking "How are you feeling?" on Leikert scale (mean, median, standard deviation, variability)
- Responses to DAQ on the DAQ app (cumulative score and individual domains mean, median, and standard deviation; variability of the responses and adherence to daily reporting)

### 8.2 SAFETY AND OTHER ASSESSMENTS

Before participating in the study, subjects will be asked about history of intolerance to albuterol. The study team will also confirm that the participant is using albuterol on a regular basis (defined as at least one puff weekly for each of the last four weeks). If the safety of albuterol use cannot be assured, the subject will be excluded from the study. If any AE's or SAE's are detected, they will be followed by the investigator until symptoms have resolved.

### 8.3 ADVERSE EVENTS, ADVERSE DEVICE EFFECTS, SERIOUS ADVERSE EVENTS AND SERIOUS ADVERSE DEVICE EFFECTS

---

### 8.3.1 DEFINITION OF ADVERSE EVENTS (AE) AND ADVERSE DEVICE EFFECTS (ADE)

An adverse event means any untoward medical occurrence associated with the use of an intervention in humans, whether or not considered intervention-related (21 CFR 312.32 (a)). Preexisting condition (i.e., a disorder present before the adverse event reporting period started) should not be reported as an adverse event unless the condition worsens or episodes increase in frequency during the adverse event reporting period. This is particularly relevant for subjects with COPD who may have substantial symptoms at baseline.

An adverse device effect is an adverse event related to the use of an investigational medical device or combination product. This includes adverse events resulting from insufficient or inadequate instructions for use, deployment, implantation, installation, operation, or any malfunction of the investigational medical device, including any event resulting from user error or from intentional misuse of the investigational medical device.

---

### 8.3.2 DEFINITION OF SERIOUS ADVERSE EVENTS (SAE)

An adverse event (AE) or suspected adverse reaction is considered "serious" if, in the view of the investigator, it results in any of the following outcomes: death, a life-threatening adverse event, inpatient hospitalization or prolongation of existing hospitalization, a persistent or significant incapacity or substantial disruption of the ability to conduct normal life functions, or a congenital anomaly/birth defect. Important medical events that may not result in death, be life-threatening, or require hospitalization may be considered serious when, based upon appropriate medical judgment, they may jeopardize the participant and may require medical or surgical intervention to prevent one of the outcomes listed in this definition.

A serious adverse device effect is an adverse device effect that has resulted in any of the consequences characteristic of a serious adverse event.

Generally, adverse events reported from clinical trials associated with hospitalization or prolongation of hospitalization are considered serious. Any initial admission (even if less than 24 hours) to a healthcare facility meets these criteria. Admission also includes transfer within the hospital to an acute/intensive care unit (e.g., from the psychiatric wing to a medical floor, medical floor to a coronary care unit, neurological floor to a tuberculosis unit).

Because of the nature of the disease population being studied, and the fact that part of the study includes evaluating subjects experiencing a COPD exacerbation with may require hospitalization, hospitalization will NOT obligatorily be considered an SAE for this study. Hospitalization will be reported as an SAE if, in the discretion of the investigator, it is temporally related to albuterol use.

Hospitalization does not include the following:

- Rehabilitation facilities;
- Hospice facilities;
- Respite care (e.g., caregiver relief);
- Skilled nursing facilities;
- Nursing homes;
- Same day surgeries (as outpatient/same day/ambulatory procedures).

Hospitalization or prolongation of hospitalization in the absence of a precipitating, clinical adverse event is not in itself a Serious Adverse Event. Examples include:

- Admission for treatment of a preexisting condition not associated with the development of a new adverse event or with a worsening of the preexisting condition (e.g., for work-up of persistent pretreatment lab abnormality);
- Social admission (e.g., subject has no place to sleep);
- Administrative admission (e.g., for yearly physical exam);
- Optional admission not associated with a precipitating clinical adverse event (e.g., for elective cosmetic surgery);
- Preplanned treatments or surgical procedures should be noted in the baseline documentation for the entire protocol and/or for the individual subject.

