- **Not Related** – The AE is completely independent of study intervention administration, and/or evidence exists that the event is definitely related to another etiology. There must be an alternative, definitive etiology documented by the clinician. As noted in 8.3.2, because of the nature of the disease population being studied, and the fact that that part of the study includes studying subjects experiencing a COPD exacerbation which may require hospitalization, hospitalization will NOT obligatorily be considered an SAE for this study. Hospitalization will be reported as an SAE if, in the discretion of the investigator, it is temporally related to albuterol use.

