### 8.3.5 ADVERSE EVENT REPORTING

In keeping with good clinical practice or good pharmacovigilance practice, and 21 C.F.R. Part 314 as the case may be, the external investigator will be required to report and notify the Teva Pharmaceuticals (Teva) of all situations mentioned below, within twenty-four (24) hours from receiving information of the situation. The event will be reported to Teva by submitting the collected information to the Teva Local Safety Officer. The event will also be reported to the FDA, Institutional Review Boards (IRBs), and any other collaborators/investigators according to national, and local safety reporting requirements.

- (a) All related Serious Adverse Events
- (b) All Serious Adverse Device Effects
- (c) Any exposure of a pregnant study participant to the study drug within thirty (30) days of exposure
- (d) Any medical event which may reasonably be believed to impair the integrity, validity or ongoing viability of the study

Each adverse event is to be classified by the investigator as serious or non-serious. This classification determines the reporting procedures to be followed. If a serious adverse event occurs, expedited reporting will follow FDA and IRB regulations. If an adverse event is both serious and unexpected, reporting will follow IRB reporting regulations as appropriate. SAEs are reportable from the time that the subject provides informed consent, which is obtained prior to the subject's participation in the trial (i.e., prior to undergoing any trial-related procedure through and including 24 hours after the final call). Any serious adverse event occurring at any other time during the study must be promptly reported if a causal relationship to study drug is suspected.

If a serious adverse event occurs, the Institutional IRB will be notified within five business days of awareness of the event by the investigator. The study coordinator may initiate the IRB notification, but it must be filed by the study investigator or co-investigators. If the serious adverse event is fatal or life threatening, notification to the Institutional IRB must be made within 24 hours, irrespective of the extent of available adverse event information. This timeframe also applies to additional new information (follow-up) on previously forwarded serious adverse event reports.

The MedWatch 3500A form should be utilized to report serious adverse events to the FDA.

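### The hospitalization exemption from SAE status covers every admission, although the reason given for it covers only COPD exacerbations

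*Combined protocol and SAP*

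**What the plan says.** Section 8.3.2 lists the outcomes that make an adverse event serious, among them "inpatient hospitalization or prolongation of existing hospitalization". A later paragraph on admissions adds: "Any initial admission (even if less than 24 hours) to a healthcare facility meets these criteria". Neither statement depends on whether the event was related to treatment.

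The next paragraph makes an exception for this study. Its reason is the disease population and the fact that "part of the study includes evaluating subjects experiencing a COPD exacerbation with may require hospitalization". Its operative words are "hospitalization will NOT obligatorily be considered an SAE for this study", followed by "Hospitalization will be reported as an SAE if, in the discretion of the investigator, it is temporally related to albuterol use". The exception is not confined to exacerbation admissions.

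Section 8.3.3.2 repeats the rule under the Not Related grade of the causality scale, introduced by "As noted in 8.3.2, because of the nature of the disease population being studied". In 8.3.5, manufacturer reporting has its own relatedness filter: "All related Serious Adverse Events".

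**The concern.** An exemption should reach no further than its reason. Exacerbation admissions are expected here, because the study enrols patients at risk of AECOPD and describes what happens around such events. There is a fair case for not sending each one as an expedited report. That case does not extend to an admission for a fracture or a stroke, yet the wording takes these in.

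The condition that restores mandatory SAE reporting is also of the wrong kind. Seriousness describes what happened to the patient, and relatedness describes why. The plan keeps the two apart elsewhere: 8.3.1 defines an adverse event without regard to causality, and 8.3.3.2 grades causality on its own five-level scale. Under the exemption, an investigator's view on timing relative to albuterol decides whether an admission must be called serious.

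What is at stake is the completeness of the SAE listing and prompt notice to the IRB. Section 10.1.6 places safety oversight with the principal investigators alone, so the IRB is an important outside check.

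**Working it through.** No arithmetic applies, and the plan states no figure on this point. The check is to set the rules side by side and follow cases through them.

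**Inputs**

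- 8.3.2, first paragraph: seriousness is set by outcome, and hospitalization is one of several sufficient outcomes.
- 8.3.2, exception paragraph: the obligation is lifted for hospitalization without qualification. SAE reporting is required if the admission is judged temporally related to albuterol.
- 8.3.2, closing list: admissions with no precipitating adverse event (social, administrative, elective) are not SAEs in any case.
- 8.3.3.2: relatedness is graded separately, and timing is already one of its inputs.
- 8.3.5: the serious or non-serious label sets the reporting route. SAEs go to the IRB within five business days, with no relatedness condition in that sentence, or within 24 hours if fatal or life-threatening. Non-serious AEs go to the IRB annually.
- 8.3.4: all AEs on study are documented whatever their relationship to treatment.

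**Cases**

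| Admission | Serious by outcome? | Must it be an SAE after the exception? | IRB route that can follow |
|---|---|---|---|
| AECOPD, judged not temporally related, no other criterion | Yes | No | Annual |
| Non-COPD, judged temporally related | Yes | Yes | Five business days |
| Non-COPD, judged not temporally related, no other criterion | Yes | No | Annual |
| Non-COPD, fatal or life-threatening | Yes, on another criterion too | Yes, on that criterion | 24 hours |
| Social or elective, no adverse event | No | No | None as an SAE |

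The first row is what the exception was written for. Those admissions are also counted elsewhere, because Section 3 lists exacerbation-associated hospitalizations as an exploratory outcome and 9.4 plans descriptive statistics for them. The third row is the gap. The stated reason does not cover it, the wording does, and no outcome counts non-COPD admissions separately. They appear only as AEs.

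**Relatedness applied more than once.** Timing relative to albuterol can decide whether the admission must be called serious. Timing then enters the causality grade in 8.3.3.2, and that grade decides manufacturer reporting in 8.3.5. Only the last two uses are needed. The first also has no time window, and under 6.1.2 albuterol is taken as needed, so the two sites could classify the same event differently.

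**The case against.** The strongest defence is that this is a deliberate exception with little consequence. Much of that stands.

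- A reader might infer that admissions cannot be SAEs unless related to albuterol. The text does not say so. It removes the obligation and uses a plain conditional, not an only-if, so an investigator may still class an unrelated admission as serious.
- A reader might infer that 8.3.2 contradicts itself. The paragraph on admissions is framed as a general statement, and what follows is marked as specific to this study. It is an exception, and the fault lies in its breadth.
- A reader might infer that an admission caused by a device problem would be missed. The documents do not support this. Section 8.3.2 defines serious adverse device effects separately, and 8.3.5 requires them to be notified to the manufacturer within 24 hours.
- A reader might infer that the test works in reverse, catching exacerbation admissions because rescue use rises around them. Section 2.2 says only that SABA use may herald an exacerbation. With no time window and no data on use before admission, this is conjecture about how investigators will judge.
- Manufacturer reporting would hardly change, because it already covers only related SAEs.
- No interim analysis (9.4.2) depends on SAE counts, and the safety analysis (9.4.1) is a simple categorization of AEs.

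These points limit the consequence. None supplies a reason for exempting non-COPD admissions, and none explains why seriousness should wait on a timing judgment.

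**Conclusion.** The point holds in a limited form. The exemption is wider than its stated reason, and it ties a seriousness label to a judgment that the plan makes separately elsewhere. The affected group is admissions that were precipitated by a non-COPD adverse event, judged not temporally related to albuterol, meet no other seriousness criterion, and are not classed as SAEs at the investigator's discretion. For these, the label can change from serious to non-serious and IRB notice from five business days to annual. Capture on the AE page of the CRF is unaffected.

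The number of such admissions cannot be estimated from the documents. Planned follow-up is about 60 × 3/12 = 15 patient-years, but no rate of non-COPD admission is given, nor how often investigators would judge one unrelated. Any count would be an assumption, and the conclusion does not need one. It rests on the text being applied as written. FDA reporting is left to regulations that the documents do not reproduce, so nothing is concluded about it. This is a modest defect in safety reporting, and worth correcting because correction is cheap.

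**What to change.** Change the exception paragraph in 8.3.2 and its repetition in 8.3.3.2 together:

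1. Limit the exemption explicitly to admissions for AECOPD. Record and tabulate these as study outcome events, with expedited reporting only if judged related. Say that an AECOPD event meeting another seriousness criterion remains an SAE.
2. State that every other admission precipitated by an adverse event is serious by outcome, as in the first paragraph of 8.3.2. Keep the existing exclusions for social, administrative and elective admissions.
3. Remove the test of temporal relation to albuterol from the seriousness definition. Assess relatedness only through the 8.3.3.2 scale, and apply it only at the reporting step in 8.3.5.
4. Because reporting would then turn on the word related, state which of the five grades count as related for 8.3.5.

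This keeps the aim of not sending expedited reports for expected exacerbations. The cost is a wording amendment in two places with a line added in 8.3.5, IRB approval of it, and a few more SAE forms for non-COPD admissions. The outcome analyses do not change.
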